### 8.2.2 Visit 2 (Phone Visit)

A study staff member will telephone each patient or caregiver on Day 3 or Day 4 of treatment. The information obtained at this “phone visit” will be recorded in the Visit 2 page of the EDC. Study staff will ask about and record any AEs and any changes in concomitant medications since Visit 1. Study staff will also ask about study medication compliance. Patients or caregivers will also be asked if otitis symptoms are improving or worsening. A specific questionnaire to obtain all these information will be used.

Patients who report no improvement in otitis symptoms will be asked to come in for an unscheduled visit as soon as possible. At this visit, the Investigator will choose one of the two following options for the patient:

1. Continue the patient in the study. The present visit will be recorded as an unscheduled visit. The patient should continue taking study medication without interruption. A debridement of the ear and placement of otowick may be needed.
2. Discontinue study medication. The present visit will be recorded as Visit 3, the End of Treatment visit. The patient will be withdrawn from the study and may be treated with other medication (standard treatment) as appropriate at investigator's discretion. The clinical outcome for the patient will be recorded as Treatment Failure.

If a patient has unilateral AOE at baseline, but develops AOE of the contralateral ear subsequently during the study, then at Visit 2 or at unscheduled visit prior to Visit 3, the investigator or designee will obtain a second kit number (with the same medication) through the IWRs to treat the contralateral ear. This information will be included in the Comments page and Resupply or replacement page of the EDC, and will not be considered as an AE.

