#### **8.2.3      Visit 3**

Visit 3 will take place between Day 8 and Day 10, or within 2 days of early discontinuation of study treatment.

Adverse events and concomitant medications will be recorded and vital signs will be assessed.

Brighton grading, otalgia, edema, and otorrhea will be evaluated as described in Appendix 2, Sections 7.1.1.1, 7.1.1.2, 7.1.1.3 and 7.1.1.4. Overall Clinical Outcome will be evaluated by the Investigator as described in Section 7.1.1.5. A microbiological culture of ear discharge (if discharge is present) will be taken as described in Section 7.1.2.

If patient took rescue medication (see Section 6.7.2) prior to this visit, the ear discharge will not be collected, because patient will be considered Treatment Failure.

Used and unused study medication containers will be collected from the patient or caregiver by a member of the study staff.

The patient diary will be reviewed to determine study medication compliance as described in Section 6.6.

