4.4 Analysis Populations

There will be 6 populations defined for this study: Safety, Clinical intent-to-treat (CITT), Microbiological intent-to-treat (MITT), MITT-PA/SA, CPP, and MPP.

The **Safety population** will include all patients who received any study medication.

The **CITT population** will include all patients who were randomized.

The **MITT population** will include all CITT patients whose Visit 1 microbiological culture yields 1 or more pathogens, as defined in Section 4.7.2.

The **MITT-PA/SA population** will include the pathogen positive subset of the CITT population which includes all patients who received study medication and had culture positive for *P. aeruginosa* and/or *S. aureus* at baseline in the evaluable ear.

The **CPP population** will include all CITT patients who:

- Satisfied all inclusion and exclusion criteria;
- Had analysis results from Visit 1 otorrhea sample;
- Did not receive any prohibited concomitant medications. Note if a patient receives prohibited medication on or after receiving rescue medication and does not have any other major protocol deviations, the patient will be included in the CPP;
- Did not have any other major protocol violations;
- Completed Visit 3 and Visit 4 (unless the patient was deemed a clinical failure at an earlier visit than Visit 4);
- Had compliance rates between 80% and 120% as defined in Section 4.6 (patients who are deemed Clinical Failures are to be included if they had compliance rates between 80% and 120% during the first 3 days of study treatment); and
- Received at least 4 doses of study medication during the first 72 hours.

The **MPP population** will include all CPP patients whose Visit 1 microbiological culture yields 1 or more pathogens and who had microbiological results (when patient has material to culture) from Visit 2 and/or Visit 4 unless the patient was deemed a clinical failure at an earlier visit than Visit 4.

For the CITT, MITT and MITT-PA/SA populations, the treatment group of a patient will be determined by the treatment group to which the patient was randomized.

Effective Date: [REDACTED]
Related to: [REDACTED]

CONFIDENTIAL

Project Document Version No. 2.0
Project Document Effective Date: Date of last signature

Page 12 of 34

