4.7.1.1 Handling of Dropouts or Missing Data

Patients with missing efficacy data or indeterminate outcomes will be considered as treatment failures for efficacy analyses.

For the primary endpoint, patients who discontinued for lack of efficacy or rescue medication use will be considered as treatment failure.

Patients who take rescue medication, discontinue or are lost to follow up, and for whom the pain persists at the time of the last observation, will be censored at maximum length (Day 17) in those cases when the diary information is not available.

To explore the effect of the handling of the missing data and assess the robustness of the efficacy results, a complete case analysis will be carried out (i.e. all efficacy analyses will be repeated on actual values i.e. without imputation of the missing data) as sensitivity analysis on the MITT population.

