4.7.2 Primary Efficacy Variable – *Therapeutic Response*

The primary endpoint for the assessment of efficacy is therapeutic response at Visit 3 in the MITT-PA/SA population. Efficacy analyses of the primary endpoint will also be conducted on the MITT, MPP CITT and CPP populations.

Therapeutic cure is the combined clinical and microbiological cure. Clinical and microbiological cure will be considered achieved if edema, otalgia, and otorrhea are resolved with no further requirement of antimicrobiological therapy and bacteriological response is Eradication or Presumed Eradication.

Overall Clinical Outcome is based on the Total Signs/Symptoms Scale (TSSS), which is calculated by the sum of otalgia score + edema score + otorrhea score. Clinical cure is a TSSS equal to 0.

Otalgia is the level of pain in the ear and is measured on a scale of 0 to 3. It will be assessed as:

- Severe (3) if it interferes with activities of daily living;
- Moderate (2) if it causes discomfort but does not interfere with activities of daily living;
- Mild (1) if there is awareness of pain but not much discomfort

- Absent (0) if there is total absence of pain.

Edema is the level of swelling in the ear and is measured on a scale of 0 to 3. It will be assessed as:

- Severe (3) if the tympanic membrane is not visible because of swelling;
- Moderate (2) if the tympanic membrane is partially visible;
- Mild (1) if there is some swelling but the tympanic membrane is fully visible;
- Absent (0) if there is no visible swelling.

Otorrhea is the discharge from the ear and is measured on a scale of 0 to 3. It will be assessed as:

- Severe (3),
- Moderate (2),
- Mild (1),
- Absent (0).

Bacteriological response will be categorized for each patient based on the microbiological culture results. Positive results will be categorized into three groups: target pathogen, non-target pathogen, and non-pathogen. For analysis purposes, patients with a target pathogen or non-target pathogen will be considered to be culture positive for a pathogen. Negative results and non-pathogen positive results will be considered to be culture negative for a pathogen. For any patient with a culture positive for a pathogen at Visit 1, bacteriologic response at Visits 3 will be classified as:

- Eradication if the culture does not show growth of any pathogen;
- Presumed Eradication if there is no material to culture and the Overall Clinical Outcome is Clinical Improvement or Clinical Cure as defined above;

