Overall Clinical Outcome is based on the TSSS, which is calculated by the sum of otalgia score + edema score + otorrhea score. Patients will be allocated to one of the following categories for Overall Clinical Outcome:

1. Clinical Cure: TSSS is 0
2. Clinical Improvement: TSSS is different than 0 but lower than the previous visit
3. Clinical Failure: TSSS does not meet the definitions of Clinical Cure or Clinical Improvement.
4. Indeterminate: Discontinued (for reasons other than Clinical Failure) or lost to follow-up

Overall clinical outcome will be summarized by treatment group and visit in terms of proportion in each category at each visit.

Responses will be categorized into two groups for analysis. Clinical improvement, Clinical Failure, and indeterminate will be collapsed into a single category: Clinical Failure. Overall clinical outcome will be analyzed using the same method as the primary efficacy endpoint. A Pearson’s Chi Squared test for independence will be used to test that there is no difference between the combined treatment and each individual component at Visits 3 and 4.

If a patient took rescue medication prior to Visit 3, the response will be considered a clinical failure at Visit 3. Similarly, if a patient took rescue medication prior to Visit 4, the response will be considered a clinical failure at Visit 4.

A by-patient listing of overall clinical outcome will be provided.

Microbiological Outcome

Microbiological Outcome is described in Section 4.7.2.

Microbiological outcome will be summarized by treatment group and visit in terms of proportion in each category at each visit.

If a patient took rescue medication prior to Visit 3, the response will be considered a failure at Visit 3. Similarly, if a patient took rescue medication prior to Visit 4, the response will be considered a failure at Visit 4.

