Responses will be summarized in terms of a 3-level response. Responses of Eradication or Presumed Eradication will be categorized as favorable. Responses of Persistence, Presumed Persistence, Superinfection, Reinfection, and Recurrence will be categorized as unfavorable. Indeterminate responses will be categorized as indeterminate. The proportion of patients with a favorable response at Visit 3 and Visit 4 will be compared between the Ciprofloxacin plus Fluocinolone acetonide and the Fluocinolone acetonide and between Ciprofloxacin and Fluocinolone acetonide treatment groups by using the same chi-squared test as the primary efficacy endpoint.

Microbiological outcome will also be presented by pathogen (*P. aeruginosa*, *S. aureus*, *T. otitidis*, and Other). The per-pathogen microbiological outcome will be derived for each pathogen identified at baseline based on the following classification:

- Eradication: elimination of pathogen identified in Visit 1 culture evidenced by the absence of that pathogen in a subsequent culture
- Presumed Eradication: elimination of pathogen identified in Visit 1 culture evidenced by the absence of any purulent discharge from which to obtain a subsequent culture in patients whose signs and/or symptoms of infection has improved or resolved
- Persistence: continued presence of pathogen identified in Visit 1 culture evidenced by the isolation of that pathogen in a subsequent culture
- Presumed Persistence: continued presumed presence of pathogen identified in Visit 1 culture when; the isolation of that pathogen in a subsequent culture was not performed, or a culture result was not available, in a patient with persistent or worsening signs and/or symptoms of infection
- Recurrence: if there is a reappearance of a pathogen (originally isolated at Visit 1) at Visit 4 eradicated or presumably eradicated at Visit 3

- Indeterminate: if none of the above definitions are met and the outcome cannot be determined

Note that new pathogens identified after Visit 1 do not have a per-pathogen outcome, the presence of a new pathogen after Visit 1 will be included in the overall microbiological response only.

A by-patient listing of microbiological outcome will be provided.

Brighton Grading

Brighton grading will be assessed at Visits 1, 3 and 4. For consistency, the same individual should perform the assessments at all 3 visits, if possible. Brighton grading will be assessed as:

- Grade 0: Normal

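### A patient stopped for no improvement is a Treatment Failure in protocol 8.2.2, but the TSSS rule can give the same patient a favorable microbiological outcome at Visit 3

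*Protocol*

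**What the plan says.** Protocol 8.2.2 (also the synopsis and section 4.1) covers patients who report no improvement at the Visit 2 call and are seen in person. If study medication is stopped, "The present visit will be recorded as Visit 3, the End of Treatment visit", the patient is withdrawn, and "The clinical outcome for the patient will be recorded as Treatment Failure".

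Protocol 8.2.3 then says of Visit 3, with no exception for patients stopped early: "Overall Clinical Outcome will be evaluated by the Investigator as described in Section 7.1.1.5". Section 7.1.1.5 and SAP 4.7.3 have four categories: Cure, Improvement, Failure and Indeterminate. Treatment Failure is not among them. The second is worded "Clinical Improvement: TSSS is different than 0 but lower than the previous visit".

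For the bacteriologic response at Visit 3, SAP 4.7.2 has "Presumed Eradication if there is no material to culture and the Overall Clinical Outcome is Clinical Improvement or Clinical Cure as defined above". The same section assigns Presumed Persistence when the outcome is Clinical Failure and no culture was done. For analysis, SAP 4.7.3 states "Responses of Eradication or Presumed Eradication will be categorized as favorable", and it compares the favorable proportion between each ciprofloxacin arm and fluocinolone.

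The safeguard in SAP 4.7.1.1 is limited to one endpoint: "For the primary endpoint, patients who discontinued for lack of efficacy or rescue medication use will be considered as treatment failure".

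**The concern.** The two sets of rules can give opposite microbiological results for the same patient at the same visit. A patient judged to have failed and taken off study medication can be scored as having had the pathogen eradicated, only because the ear was dry and the score fell by a point. The programmer has to choose between the readings, and the documents do not say which one governs.

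At stake is the Visit 3 microbiological outcome: the two comparisons with fluocinolone and the response-category tables. If early stopping with a dry ear is more common in the arm without an antibiotic, the literal rule narrows those contrasts.

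A second question concerns the per-protocol sets. A withdrawn patient does not complete Visit 4, and SAP 4.4 excuses this only with the words "unless the patient was deemed a clinical failure at an earlier visit than Visit 4". If that depends on the TSSS category, a patient whose score fell at all, dry ear or not, could lose the exemption and leave CPP and MPP. The primary endpoint is also analysed in those two sets.

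**Working it through.** The plan gives no figure on this point to reproduce, and the sample-size calculation plays no part. The check is of the classification rules.

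**1. Inputs.** Entry (protocol 5.1) requires otalgia 2–3, edema 2–3 and otorrhea 1–3, so there are 2 × 2 × 3 = 12 baseline patterns. Visit 2 is a telephone call without scoring, so the previous scored visit is Visit 1. A dry ear is not cultured (protocol Table 1, footnote c).

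**2. Dry ear, pain and edema unchanged.** Write o, e and r for baseline otalgia, edema and otorrhea. Visit 3 TSSS minus Visit 1 TSSS = (o + e + 0) − (o + e + r) = −r, a fall of 1 to 3 points. The Visit 3 score is o + e, at least 4, so it is not zero. All 12 of 12 patterns are Clinical Improvement. Example: 3 + 3 + 1 = 7 becomes 3 + 3 + 0 = 6, with pain and edema still severe.

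**3. Dry ear, any pain and edema score.** 12 baseline patterns × 16 otalgia/edema pairs = 192. Removing the 12 with TSSS 0 leaves 180. The score fails to fall in 6, all with worse pain or edema: 3 from baseline 2+2+1, and 1 each from 2+2+2, 2+3+1 and 3+2+1. The other 174 are Clinical Improvement.

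**4. The two readings for the patient in step 2.**

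| Item | Label read as Clinical Failure | TSSS rule taken literally |
|---|---|---|
| Overall Clinical Outcome, Visit 3 | Clinical Failure | Clinical Improvement |
| Bacteriologic response, no culture | Presumed Persistence | Presumed Eradication |
| SAP microbiological group | unfavorable | favorable |
| Therapeutic cure, Visit 3 | failure | failure (TSSS above 0; also SAP 4.7.1.1) |
| Clinical cure, Visit 3 | failure | failure (Improvement collapsed into Failure, SAP 4.7.3) |
| Sustained microbiological cure, Visit 4 outcomes | failure (withdrawn, missing) | failure (withdrawn, missing) |
| CPP/MPP exemption for a missing Visit 4 | yes | unclear |

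**5. Overrides.** None changes the favorable entry. The lack-of-efficacy rule covers the primary endpoint only. The rescue rule for microbiological outcome (SAP 4.7.3) needs rescue before Visit 3, whereas here any other treatment follows the decision made at that visit. The missing-data rule does not apply, because Visit 3 data exist. Protocol 4.1 assesses a patient given other treatment for the evaluable ear as a treatment failure, but names no visit or endpoint.

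**6. Size.** Let a be the proportion of an arm stopped under 8.2.2, and b the share of those with a dry ear and a lower, non-zero TSSS. The literal rule raises that arm's favorable rate by s = a × b and changes the contrast by s(ciprofloxacin arm) − s(fluocinolone). The documents give neither a nor b. Assuming a of 5–30% and b of 25–75%:

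- Lowest: 0.05 × 0.25 = 1.25 points (0.9 of 75 patients, 1.9 of 150).
- Highest: 0.30 × 0.75 = 22.5 points (16.9 of 75, 33.8 of 150).
- If s is equal in both arms, the contrast does not change.
- If a is 20% on fluocinolone and 5% on ciprofloxacin with b = 50% in both, the change is 2.5 − 10.0 = −7.5 points.

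The 75 and 150 are the planned evaluable (MITT) numbers. MITT-PA/SA is narrower, so patient counts there would be no larger.

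**The case against.** The strongest reply is that the intent can be read from the text. Section 8.2.2 is the specific rule for this patient and calls the clinical outcome a failure. The Indeterminate category is reserved for patients who discontinue for reasons other than Clinical Failure, which implies that stopping for failure is itself Clinical Failure. The Presumed Persistence rule in protocol 7.1.2 and SAP 4.7.2 expressly covers patients who discontinue early. The per-pathogen rules in SAP 4.7.3 also give Presumed Persistence where signs or symptoms persist, which fits the 3 + 3 + 0 patient at least as well as improved does. On this view one mapping sentence is missing and nothing more.

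That is probably what was meant, but the plan does not say so. The patient-level rule is stated, applies to this visit without exception and gives the opposite result. The per-pathogen wording applies to a separate table and does not override it.

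Other parts of the reply stand. The Visit 3 microbiological outcome is among the endpoints that protocol 10.1.10.2 makes supportive only. The rule applies in all arms, so only a between-arm difference moves the contrast. On the per-protocol sets, a patient recorded as Treatment Failure may well count as deemed a clinical failure, and membership is settled at blinded review. That part is an ambiguity, not a demonstrated loss of patients.

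**Conclusion.** The contradiction is real and its reach is limited. Stated rules give a favorable microbiological result at Visit 3 to a patient whom the protocol records as a failure, in every eligible baseline pattern with a dry ear and unchanged pain and edema. The patient must be stopped early, have nothing to culture and have a lower, non-zero TSSS. Where there is discharge, the culture decides and there is no conflict.

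A reader might infer more than the documents support:

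- That the evidence for the antibiotic's contribution is compromised. That evidence rests on the primary endpoint, where the combination must beat fluocinolone alone on therapeutic cure, and the MITT-PA/SA result is protected. So are clinical cure at Visit 3 and, in practice, sustained microbiological cure and the Visit 4 outcomes.
- That 174 of 180 means about 97% of such patients. It is an unweighted count of score combinations, some implausible in a patient stopped for no improvement.
- That the steroid-only arm will gain most because corticosteroids dry the ear. Protocol 2.3 mentions otorrhea outcomes in children and animal models of otitis media, not failing ears in otitis externa.

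The size is unknown. The 1.25 to 22.5 points per arm rest on assumed rates, and the effect on each contrast is the difference between arms, which could be zero.

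**What to change.** Reconcile the passages. State in protocol 7.1.1.5 and SAP 4.7.2, 4.7.3 and 4.4 that:

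- a patient recorded as Treatment Failure under protocol 8.2.2 is Clinical Failure at Visit 3 whatever the TSSS;
- the bacteriologic response is Presumed Persistence when no culture is available, and an available culture result still decides;
- the patient counts as a clinical failure for the CPP and MPP exemptions.

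The lack-of-efficacy sentence in SAP 4.7.1.1 should not be widened to all responder endpoints. That would turn an Eradication documented by culture into a microbiological failure and merge outcomes that the plan keeps separate.

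The change concerns outcome classification only and leaves patient management as it is. It costs a few sentences. No new data are needed, because protocol 5.3 already has the reason for stopping recorded. The downside is slightly lower microbiological cure rates at Visit 3. It should be settled before database lock, in line with SAP 4.11.

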#### **8.2.3      Visit 3**

Visit 3 will take place between Day 8 and Day 10, or within 2 days of early discontinuation of study treatment.

Adverse events and concomitant medications will be recorded and vital signs will be assessed.

Brighton grading, otalgia, edema, and otorrhea will be evaluated as described in Appendix 2, Sections 7.1.1.1, 7.1.1.2, 7.1.1.3 and 7.1.1.4. Overall Clinical Outcome will be evaluated by the Investigator as described in Section 7.1.1.5. A microbiological culture of ear discharge (if discharge is present) will be taken as described in Section 7.1.2.

If patient took rescue medication (see Section 6.7.2) prior to this visit, the ear discharge will not be collected, because patient will be considered Treatment Failure.

Used and unused study medication containers will be collected from the patient or caregiver by a member of the study staff.

The patient diary will be reviewed to determine study medication compliance as described in Section 6.6.

#### **8.2.4      Visit 4**

Visit 4 will take place between Day 15 and Day 17. All patients (except those who have been withdrawn from the study or have withdrawn their consent as described in Section 5.3) are expected to attend Visit 4 (TOC).

Adverse events and concomitant medications will be recorded, and vital signs will be assessed.

Brighton grading, otalgia, edema, and otorrhea will be evaluated as described in Appendix 2, Sections 7.1.1.1, 7.1.1.2, 7.1.1.3, and 7.1.1.4. Overall Clinical Outcome will be evaluated

by the Investigator as described in Section 7.1.1.5. A microbiological culture of ear discharge (if discharge is present) will be taken as described in Section 7.1.2.

If patient took rescue medication (see Section 6.7.2) prior to this visit, the ear discharge will not be collected, because patient will be considered Treatment Failure.

Upon completing Visit 4, the patient will have completed his or her participation in the study.

